Aim #4: Conduct a pilot randomized controlled trial (RCT) of *Maisha* to examine 1) feasibility and acceptability in an ANC setting, and 2) impact on early retention in PMTCT, HIV disclosure, and constructs of HIV stigma. *Methods:* We will conduct a pilot RCT with 150 women, both HIV-infected (n=25 *Maisha*; 25 Standard of Care, SoC) and HIV-uninfected (n=50 *Maisha*; 50 SoC). Women will be randomized to receive either the SoC HIV testing and counseling, or SoC plus the *Maisha* intervention. Participants will complete a baseline survey and a follow-up survey at 3 months. Surveys will include measures for health outcomes (e.g., HIV care engagement, adherence to ART, depression, HIV testing), stigma outcomes (e.g., anticipated stigma, enacted stigma, internalized stigma), and other secondary outcomes or potential covariates (e.g., partner support, attitudes to ART, intimate partner violence). A subset of 15 HIV-infected intervention patients will participate in a qualitative in-depth interview at 3 months to provide feedback on the intervention. Clinical data will be abstracted from the medical records of participants completing the 3-month survey.

Overview and timeline

This 5-year study (2016-2021) seeks to understand and inform the implementation of the Option B+ protocol for PMTCT care in the Kilimanjaro Region of Tanzania, and develop an intervention to support women who are newly pregnant and being tested for HIV. The work is being completed in diverse clinical settings, using a multi-methods approach informed by the Consolidated Framework for Implementation Research (Table 1).

Table 1: Study timeline

AIMS	METHODS	YEAR 1				YEAR 2				YEAR 3				YEAR 4				YEAR 5				
		1	2	3	4	1	2	3	4	1	2	3	4	1	2	3	4	1	2	3	4	
Aim 1: Examine implementation of B+ for postpartum care engagement	Observations to assess services and fidelity to protocol																					
	Key informant interviews to assess process and barriers																					
	Record review to assess care engagement outcomes (n=512)																					
Aim 2: Identify factors that impact postpartum care engagement	Enroll pregnant women on ART at clinic sites (n=200)																					
	Follow-up interviews at 3m and 6m postpartum with possible additional surveys up to 2 years postpartum																					
	In-depth interviews to explore care engagement process (n=24)																					

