Feasibility and acceptability of the intervention and the associated trial will be described by: recruitment and retention patterns, participant satisfaction, fidelity, and implementation cost. Retention will be monitored to calculate the percentage of participants who attend the 1-week *Maisha* session (in intervention) and the 3-month assessment, to document barriers to attendance for participants, and to examine differences between those who attend and those who do not. Participant satisfaction data at the 3-month follow-up will be described, with >80% satisfaction used as a metric of acceptability. Qualitative data will be thematically coded for focus on participants' perceptions of the intervention, suggestions for changes, and feasibility moving forward. The fidelity to the intervention will be assessed by examining the percentage of components from the manualized content that are covered in each session. To estimate the cost of the intervention, we will track the time for training and delivery, as well as actual costs incurred. Qualitative feedback and QA data will be used to revise and improve the curriculum for the future.

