Potential efficacy will be examined by analyzing separate outcomes for HIV-infected and HIV-uninfected women. For HIV-infected women, we are interested in differences between conditions in health outcomes (retention in PMTCT, medication adherence, depression) and stigma (anticipated stigma, internalized stigma and HIV disclosure). For HIV-uninfected women, we are interested in differences between conditions in stigma (attitudes to PLWH and anticipated stigma), as well as willingness to test for HIV in the future. For outcomes where there is a baseline measure, mixed-effects regressions will be used to model pre-post differences within and between arms, using a time by condition model specification (time, condition, and time*condition). Individual-level random intercepts will be used to account for correlation due to repeated measurement. Using a mixed-effects regression approach leaves flexibility to control for baseline outcome values that may not be balanced between groups due to small sample size, and may improve precision of treatment effect estimation. For outcomes where there is no baseline measure, we will examine differences in means or proportions with 95% confidence intervals. If we suspect, a priori, that baseline imbalance in prognostic covariates may be an issue, we will move into a regression framework. Results across outcomes will generate parameter estimates and potential ranges of values to estimate power for a future R01. This analytic approach is consistent with best practices for analysis of pilot feasibility trials. Data analysis will be led by the KCRI statistician and DGHI postdoc. To reduce bias and ensure reproducibility of results, we will discuss analytic approaches and review syntax as a team. All outcome analysis will be reviewed by an external statistician with study condition blinded (see letter from DGHI Research Design Core).

References

1. U.S. Department of State. *PEPFAR blueprint: Creating an AIDS-free generation*. Washington: U.S. Department of State; 2012.
3. Bateman C. Much ado over the new South African PMTCT guidelines. *S. Afr. Med. J.* Apr 2013;103(4):218-221.

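### For outcomes with a baseline, the only model written down estimates the arm difference in mean change; for continuous outcomes, adjusting for baseline would generally be more precise at little cost

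*Combined protocol and SAP*

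**What the plan says.** Section 10 gives one model for outcomes that have a baseline measure: a mixed-effects regression "using a time by condition model specification (time, condition, and time*condition"), with a random intercept per woman. It defends the mixed-effects approach because it "leaves flexibility to control for baseline outcome values that may not be balanced between groups due to small sample size", and because it "may improve precision of treatment effect estimation". No model with the baseline value as a covariate, and none with a common baseline mean, is written down. One further sentence, placed after the treatment of outcomes without a baseline, allows a move to regression if imbalance in prognostic covariates is suspected in advance. It names no covariate and no model.

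For HIV-infected women the outcomes are "health outcomes (retention in PMTCT, medication adherence, depression) and stigma (anticipated stigma, internalized stigma and HIV disclosure"). For the others, "For HIV-uninfected women, we are interested in differences between conditions in stigma (attitudes to PLWH and anticipated stigma"), together with willingness to test for HIV again. The purpose is stated as "Results across outcomes will generate parameter estimates and potential ranges of values to estimate power for a future R01".

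Under Phase 6 in Section 1, the baseline survey comes before randomisation and before the clinic's HIV test. It covers, among other things, mental health and attitudes to people living with HIV. Aim #4 says that the surveys include "stigma outcomes (e.g., anticipated stigma, enacted stigma, internalized stigma"), but the Phase 6 list of baseline content does not name anticipated stigma.

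**The concern.** The reasons given for the model are possible baseline imbalance and precision. The model as written serves neither as well as it could. It removes the whole baseline difference between arms, whereas only the part that carries forward to 3 months should be removed, and for continuous outcomes this usually costs precision. With 25 HIV-infected women per arm, imbalance by chance is likely, as the plan itself recognises.

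The outcomes affected are few. In HIV-infected women it is depression, and in HIV-uninfected women attitudes to people living with HIV, each only if scored continuously. Anticipated stigma joins them if it is asked at baseline. PMTCT retention, adherence, internalized stigma and disclosure are outside the point, because for newly diagnosed women the baseline precedes the HIV test.

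At stake are wider intervals, and estimates that depend on chance baseline differences, in results meant to inform a larger trial.

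**Working it through.** **Inputs from the documents.** Two visits; 25 v 25 HIV-infected and 50 v 50 HIV-uninfected women (Aim #4; 25 + 25 + 50 + 50 = 150); about 1000 women baselined (Section 2, Phase 6), hence about 1000 − 50 = 950 HIV-uninfected baselines, or 475 per arm. The plan has no precision or power figure to reproduce.

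**Assumptions.** The documents give no correlation, SD, scoring or expected retention; of retention they say only "Retention will be monitored to calculate the percentage of participants who attend". So rho is shown at 0.3, 0.5 and 0.7. Let k be the baseline SD divided by the 3-month SD; k = 1 unless stated.

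**1. What the stated model estimates.** With complete pairs, the interaction is a purely within-woman contrast, so it equals the difference in mean change. Three simulated data sets fitted by REML gave −0.1700, 0.0985 and 0.3641 both for the interaction and for the change-score difference. Adding the baseline value as a covariate gave the same three values, because a covariate that is constant within a woman cannot alter a within-woman contrast. With incomplete pairs this identity fails: in a simulated set with 19 of 25 followed per arm, adding the covariate moved the coefficient from 0.010 to −0.026.

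**2. Variance with complete pairs.** In units of the 3-month variance, each multiplied by 2/n:
- Change: 1 + k² − 2k·rho
- Baseline-adjusted: 1 − rho²
- Ratio: 1 + (k − rho)²/(1 − rho²), which is 2/(1 + rho) at k = 1

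| | rho 0.3 | rho 0.5 | rho 0.7 |
|---|---|---|---|
| Ratio, k = 1 | 1.54 | 1.33 | 1.18 |
| Simulated, 25 per arm (40,000 trials) | 1.51 | 1.32 | 1.15 |
| 25 / simulated ratio | 16.6 | 19.0 | 21.7 |
| 95% half-width, stated (SD) | 0.66 | 0.55 | 0.43 |
| 95% half-width, adjusted (SD) | 0.53 | 0.48 | 0.40 |
| Ratio, k = 1.4 | 2.33 | 2.08 | 1.96 |
| Simulated ratio, k = 0.7 | 1.15 | 1.03 | 0.98 |

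The half-widths are 1.96 × √(2V/25), with V = 2(1 − rho) or 1 − rho². The simulated ratios include the cost of estimating the baseline slope. The change variance relative to comparing 3-month means alone is 2(1 − rho): 1.40 at rho 0.3 and 1.00 at rho 0.5.

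**3. Where the gain disappears.** It is below 5% when |k − rho| < √(0.05(1 − rho²)): k of 0.09–0.51, 0.31–0.69 and 0.54–0.86 at the three values of rho.

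**4. Loss to follow-up.** With N baselines and n followed per arm, k = 1 and loss unrelated to outcome, the stated variance is 2[(1 − rho²)/n + (1 − rho)²/N] and the adjusted variance 2(1 − rho²)/n. The ratios are:
- 20 of 25 followed: 1.43, 1.27, 1.14 (simulated 1.40, 1.23, 1.12)
- 17 of 25 followed: 1.37, 1.23, 1.12 (simulated 1.33, 1.20, 1.09)
- HIV-uninfected, 50 followed of 475 baselined: 1.06, 1.04, 1.02
- HIV-uninfected, only the 100 followed enter: 1.54, 1.33, 1.18

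**5. Dependence on chance imbalance.** Given a baseline difference D at equal SDs, the stated estimate shifts by −(1 − rho)D. Simulated slopes were −0.70, −0.51 and −0.30, against within 0.005 of zero for the adjusted estimate. The SD of D at 25 per arm is √(2/25) = 0.283, so |D| ≥ 0.3 SD occurs in 29% of trials. At rho 0.5 that moves the estimate by 0.5 × 0.3 = 0.15 SD, against a standard error of 0.28. Averaged over randomisations, the simulated bias was within 0.004 of zero.

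**The case against.** The stated model is valid: randomisation follows the baseline survey, so the estimate is unbiased. Aim #4 puts feasibility and acceptability first, efficacy is described as potential, and no power target is set. That stands, and it limits how much weight the point can bear.

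A reader might infer that the plan ignores baseline. It does not. The interaction subtracts the baseline difference, and the text leaves room both for control of baseline values and for a conditional regression on prognostic covariates. Adjustment is therefore permitted but not specified. Neither sentence closes the gap, since neither gives a model, and with complete pairs the obvious step of adding the baseline covariate to the stated model leaves the interaction as it was.

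A reader might also infer that the R01 will be oversized. That would follow only if it were sized on the SD of change, which the plan does not say. As an illustration, for an assumed effect of 0.4 SD, 80% power and two-sided 5%, n per arm = 2(1.96 + 0.8416)²V/0.4². This gives 138, 99 and 59 on change, against 90, 74 and 51 with baseline adjustment. But the stated random-intercept model already estimates the within-woman correlation, so with similar SDs at the two visits an adjusted design could be planned from it.

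Finally, the scope is narrow, continuous scoring is assumed, and the benefit in HIV-uninfected women is only 2–6% if all roughly 950 baselines enter.

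**Conclusion.** The point holds as a modest improvement. For continuous outcomes with a baseline, the specified interaction is unbiased but generally less precise than baseline adjustment, and it moves with chance imbalance, although imbalance and precision are the plan's own reasons for the approach. In the HIV-infected stratum, with all 25 per arm followed and equal SDs, it performs like roughly 17, 19 or 22 women per arm under baseline adjustment at rho 0.3, 0.5 or 0.7. These figures rest on assumed correlation, SD ratio, retention and scoring. The gain is smaller with loss to follow-up and is little or nothing when the SD ratio is near rho. The documents do not support calling the analysis biased or invalid, and they do not establish that the later trial would be wrongly sized.

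**What to change.** For depression in HIV-infected women and attitudes to people living with HIV in HIV-uninfected women, if scored continuously, and for anticipated stigma if it is asked at baseline, define the between-arm effect as the 3-month arm difference from one of these:

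- a regression of the 3-month value on arm and baseline value, which is the simpler option and uses only women followed; or
- a mixed model with a common baseline mean (time and time*condition, no condition main effect, visit-specific variances), which also keeps women with a baseline only.

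Keep within-arm pre-post change as descriptive. Report the SD at each visit and the baseline to 3-month correlation as inputs for the R01.

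The cost is one or two sentences in Section 10 and a small change of syntax, with no new data. The mixed-model option changes the covariance structure as well as the fixed effects, so it is more than the removal of one term.
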